In the context of a prospective, randomized study with crossover, **our specific aims are to:**

1. Determine in young adults with pre- or stage I hypertension whether ULT with 300 mg of allopurinol once daily over 4 weeks will:

1a. Lower blood pressure

Hypothesis 1: Four weeks of ULT therapy will induce a greater reduction in ambulatory blood pressure levels when compared to four weeks on placebo

Hypothesis 2: ULT will induce a greater reduction in ambulatory blood pressure levels in African Americans when compared with other races/ethnicities.

1b. Induce a change in endothelial function

Hypothesis 3: Four weeks of ULT will induce an improvement in endothelial function as indexed by flow-mediated arterial vasodilation (FMD) compared to placebo.

Hypothesis 4: ULT will induce a greater increase in FMD in African Americans when compared with other races/ethnicities.

1c. Induce a change in serum levels of high sensitivity C-reactive protein

Hypothesis 5: Four weeks of ULT will induce a greater reduction in serum levels of high sensitivity C-reactive protein (hsCRP) than placebo.

Hypothesis 6: ULT will induce a greater reduction in hsCRP in African Americans when compared with other races/ethnicities.

2. Determine if the impact of ULT on hsCRP, FMD, and blood pressure is associated with the change in serum urate achieved

Hypothesis 7: Changes in hsCRP, FMD, and blood pressure will be associated with the serum urate change observed after four weeks of ULT with allopurinol compared to placebo.

We initially aimed to recruit 112 young adults (ages 18-40 years) with pre-hypertension or JNC 7 stage I hypertension³⁷ not taking antihypertensive medication. Recruitment includes men, women, African Americans, and other races/ethnicities in equal numbers. To increase generalizability and add novelty to the research question, participants will not be required to be hyperuricemic, but to have serum urate levels ≥ 5.0

mg/dL for men and 4.0 mg/dL for women. Participants will be randomized to receive allopurinol or placebo in a four-week study with crossover. This novel translational study will generate knowledge about the mechanism by which ULT lowers blood pressure and provide evidence that can be translated into clinical practice for patients with gout or high-normal urate levels and other cardiovascular risk factors, including hypertension.

C. RESEARCH STRATEGY

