Serious medical condition that at investigator's judgment precludes utilization of a fixed dose of allopurinol

*Study was amended on 10/2014 and 07/2015 to allow inclusion of individuals ages 36-40 and 18, respectively.

**Study was amended on 10/2015 to allow of inclusion of individuals on stable doses of calcium channel blockers.

E. Participant Retention

Retention of participants is central to the internal validity of the proposed study and will be an extraordinarily high priority. To increase retention, we hire engaging, attentive, and responsive staff and provide participants with as much flexibility as we can to complete their study visits. Other features used to promote high retention rates will include tracking systems and collection of information (i.e., names and telephone numbers) for two friends/family members who do not live with the study participant but would know where to find them. Once enrolled, a proactive plan for retention will be implemented that includes in person visits

every 4 weeks, and phone calls in between each visit. The following major principles and commonly used strategies to maximize retention and minimize loss to follow-up will be employed during the trial:

- Stressing the idea that participants have an active role in the research and are part of the research team
- Enhancing participant's understanding of the study's mission and the protocol
- Stressing that retention efforts begin with recruitment and are an ongoing process
- Building patient relations and patient satisfaction, with the study staff taking a central role on this effort
- Emphasizing the importance of congeniality, respectfulness and friendliness in interactions with participants
- Actively discuss with patients any questions and concerns pertaining to their condition
- Identifying potential problems and key retention factors and developing intervention strategies regarding retention
- Assessing each patient's drop out potential and intervening as needed to keep patients interested in continuing to participate
- Subjects will be paid \$25 for each completed clinic visit and flow mediated dilation procedure. In addition, subjects will receive \$100 for each complete 24-hour ambulatory blood pressure recording session. Payments will be made at the completion of each study visit's procedures. Should subjects withdraw from the study, they will be paid for the completed visits up to the date of withdrawal.

F. Study Procedures

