A database will be designed for the current study in the REDCap system. These computerized templates, are accessible through a secure web interface. Data entered into the system will be downloaded weekly and the database will have range and validity checks built in. All abnormal values will be flagged for further investigation. Research staff performing data entry will be trained in the use of the REDCap system and the study database. The study statistician will develop validity checks for outlier values, consistency, and completeness and will notify the principal investigator if issues are identified. Discrepancies will be adjudicated by consultation with the principal investigators. Once data entry is complete, the study data will be transferred to SAS statistical software and reviewed by the statistician.

16. Safety Monitoring and Reporting

The following defines the types of adverse events that study staff should inquire about at each visit. The type and possible causes of the adverse event will be discussed with the principal investigator, an examination will be conducted if deemed necessary, and it will be reported to the required parties. It is the responsibility of each and every study staff member to determine the appropriate line of action, to take the action agreed upon with the participant, and to subsequently report the event.

- Adverse Event (AE) - An AE is any unfavorable and unintended diagnosis, sign (including an abnormal laboratory finding), symptom, or disease temporarily associated with the study intervention, which may or may not be related to the intervention. AEs include any new events not present during the pre-intervention period or events that were present during the pre-intervention period which have increased in severity.

- Serious Adverse Event (SAE) - An SAE is any untoward medical occurrence that results is life-threatening, requires or prolongs hospitalization, causes persistent or significant disability/incapacity, results in congenital anomalies/birth defects, in death, or, in the opinion of the investigators, represents other significant hazards or potentially serious harm to research participants or others. All SAEs will be reported to the Safety officer (via KAI), Data Safety and Monitoring Board (DSMB), and IRB within 48 hours of the Principal Investigator becoming aware of the event.
- *Unexpected adverse event: Any adverse event, the specificity, frequency or severity of which is not consistent with either:*

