control and to compare its effects to placebo in 112 participants with prehypertension and stage I hypertension. [REDACTED] will be responsible for data safety and monitoring. As PIs they will complete and submit to the Project Advisory Committee monthly reports detailing the study progress and participant status, any adverse events, and any protocol deviations. Continuous, close monitoring of individual participant by the PIs will be assured throughout the study period. Events determined by the PIs to be serious, unanticipated problems involving risks, those not described in **Table 8. Adverse Events**, to the participants will be reported by the PIs to the IRB, DSMB, and the Safety Officer (via KAI) within 48 hours.

Table 8. Adverse Events – This document will be updated as needed.

Activities of Daily Living-ADL

Body Surface Area- BSA

Body System			
Cardiovascular	Mild	Moderate	Serious
Myocardial Infarction			All reported myocardial infarction will be classified as serious
Increased Blood Pressure	Systolic BP 140 - 159 mm Hg or diastolic BP 90 - 99 mm Hg; medical intervention indicated	Systolic BP \geq 160 mm Hg or diastolic BP \geq 100 mm Hg; medical intervention indicated	Life-threatening consequences (e.g., malignant hypertension, transient or permanent neurologic deficit, hypertensive crisis)
Hematology	Mild	Moderate	Serious
Anemia	13-10 Hb g/dl)	10-8 Hb g/dl	<8 Hb g/dl
Thrombocytopenia	150 000- 75 000/mm ³	<75,000 – 50,000/mm ³	<50,000 – 25,000/mm ³
Neutropenia	<LLN – 1500/mm ³	<1500-1000/mm ³	<1000-500/mm ³
Gastrointestinal	Mild	Moderate	Serious
Vomiting	1 - 2 episodes (separated by 5 minutes) in 24 hrs	3 - 5 episodes (separated by 5 minutes) in 24 hrs	\geq 6 episodes (separated by 5 minutes) in 24 hrs; tube feeding, TPN or hospitalization indicated
Diarrhea	Increase of <4 stools per day over baseline; mild increase in ostomy output compared to normal	Increase of 4 - 6 stools per day over baseline; moderate increase in ostomy output compared to normal	Increase of \geq 7 stools per day over baseline; incontinence; hospitalization indicated; serious increase in ostomy

Project 2: The Effects of Urate Lowering Therapy on Inflammation, Endothelial Function, and Blood Pressure (NIAMS: CORT)

			output compared to normal or death

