Other	Asymptomatic or mild symptoms; clinical or diagnostic observations only; intervention not indicated	Minimal, local or noninvasive intervention indicated; limiting age appropriate instrumental ADL	Medically significant or immediately life threatening; hospitalization or urgent intervention indicated
Musculoskeletal	Mild	Moderate	Serious
Joint pain	Mild pain	Moderate pain; limiting instrumental ADL	Serious pain; limiting self-care

Nervous	Mild	Moderate	Serious
Any patient reported event	Asymptomatic; clinical or diagnostic observations only; intervention not indicated	Moderate symptoms; limiting instrumental ADL	Serious symptoms; limiting self care ADL or death
Skin and subcutaneous tissue disorders	Mild	Moderate	Serious
Rash- characterized by a circumscribed and elevated skin lesion	Papules and/or pustules covering <10% BSA	Papules and/or pustules covering 10-30% BSA	Papules and/or pustules covering any % BSA, with life threatening consequences or death
Stevens Johnson Syndrome		Skin sloughing covering <10% BSA with associated signs (e.g., erythema, purpura, epidermal detachment and mucous membrane detachment)	Skin sloughing covering 10 - 30% BSA with associated signs (e.g., erythema, purpura, epidermal detachment and mucous membrane detachment) or death
Itch	Asymptomatic or mild symptoms; clinical or diagnostic observations only; intervention not indicated	Minimal, local or noninvasive intervention indicated	Medically significant or immediately life threatening; hospitalization or urgent intervention indicated

Hepatobiliary	Mild	Moderate	Serious
Abnormal liver enzymes	Above the upper limit to 2x ULN	2x ULN to 4X -	Greater than 4x ULN

Values and definitions derived from:

Common Terminology Criteria for Adverse Events (CTCAE) Version 4.0

Published: May 28, 2009 (v4.03: June 14, 2010) U.S. DEPARTMENT OF HEALTH AND HUMAN SERVICES

National Institutes of Health National Cancer Institute

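### In Table 8 the Nervous row leaves a mild symptomatic event without a valid grade; a low-blood-pressure row is also missing, a lesser gap

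*Combined protocol and SAP*

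**What the plan says.** Section 16, Table 8 sets three grades for each type of event.

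- **Nervous.** There is one row, "Any patient reported event". Mild is "Asymptomatic; clinical or diagnostic observations only; intervention not indicated". Moderate is "Moderate symptoms; limiting instrumental ADL". Serious requires serious symptoms that limit self-care, or death.
- **Other (inside the Gastrointestinal block) and Itch.** In both rows mild is "Asymptomatic or mild symptoms; clinical or diagnostic observations only; intervention not indicated".
- **Cardiovascular.** There are two rows, myocardial infarction and "Increased Blood Pressure". No row covers a fall in pressure or syncope, and there is no Other row for this system.

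Table 7 (Section 14b) plans a summary of adverse events that classifies each one by body system and by severity. The adverse event form in Appendix 2, Screenshot 14 shows the same two cardiovascular items and a single Nervous item.

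**The concern.** A row meant to take whatever the patient reports will mostly take symptoms. If its lowest grade admits only events without symptoms, the commonest kind of report has nowhere to go. Staff must then leave the grade blank or choose moderate. Either choice distorts the severity distribution for that body system, and different staff may choose differently.

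The row also matters because it is the natural home for light-headedness, a symptom that a fall in blood pressure could cause. Specific Aims, Hypothesis 1 states that "Four weeks of ULT therapy will induce a greater reduction in ambulatory blood pressure levels when compared to four weeks on placebo". A footnote to Table 1 records an amendment to "allow of inclusion of individuals on stable doses of calcium channel blockers". A fall in pressure is therefore foreseeable in this trial, yet Table 8 grades blood pressure only upward.

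**Working it through.** No sample size, rate or test statistic enters this point, so the check is a comparison of the rows.

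**Step 1: which nervous-system events can be graded?** Read each cell as written, with its parts applying together.

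- A finding without symptoms meets mild.
- A mild symptom with no limit on daily activities fails mild, because it is not asymptomatic. It fails moderate, because it is neither a moderate symptom nor limiting. It also fails serious. No grade fits.
- A moderate symptom that limits instrumental activities meets moderate.
- A serious symptom that limits self-care meets serious.

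Three of the four cases have a grade. The missing one is the mild symptom.

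**Step 2: is this a deliberate choice in the table?** The Other and Itch mild cells have the same three parts as the Nervous mild cell. The only difference is that they add mild symptoms to the first part. The joint-pain row also lets mild pain be graded mild. No reason is given for treating nervous-system symptoms differently, so the likeliest explanation is that the words were left out.

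**Step 3: what happens to an event related to low blood pressure?** Take the same four levels.

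- Low reading without symptoms: no row.
- Mild symptom: the Nervous row applies, but no grade fits (Step 1).
- Moderate, limiting symptom: Nervous, moderate. Nothing marks it as related to blood pressure.
- Serious symptom: Nervous, serious, with the serious adverse event route if that definition is met.

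By symptoms, 2 of 4 levels can be graded now. With the mild wording corrected, this becomes 3 of 4. As a blood-pressure event, 0 of 4 can be coded before or after that correction. Only an added row changes this.

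**Step 4: does the tabulation need both parts?** Yes. The Table 7 summary uses body system and severity together, so an event without a grade has no cell in it.

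**The case against.** The strongest reply is that these events are not lost. Staff ask about anything untoward at visits and check-ins. Appendix 3, SOP E has them query new or changed signs and symptoms, judge intensity, and record this on the adverse event form. Section 16 requires all adverse events to be reported. All of that stands: the gap is in grading, not in collection. It does not supply the missing grade in Table 8.

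It may also be said that the semicolons in the mild cell mark alternatives, so that needing no intervention would be enough. Table 8 does not say so, and the added words in the two sister rows suggest that symptoms had to be named. If both readings are possible, graders can differ.

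The form is uncertain evidence. Its drop-down options cannot be seen, and the screenshot also omits the Gastrointestinal Other row and Itch, both of which are in Table 8. The form may already carry better wording or an Other type. The finding therefore rests on Table 8. The note that Table 8 will be updated as needed makes the repair easy but does not make it.

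A reader might infer more than the documents support:

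- **That excess lowering has no coded place at all.** Moderate and serious symptoms have Nervous grades, and serious events go to the Safety Officer, DSMB and IRB within 48 hours.
- **That the definition excludes it.** Section 16 says "An AE is any unfavorable and unintended diagnosis, sign", and lowering is the hoped-for effect. An unfavorable, excessive fall is not the intended effect, however, and the definition in SOP E has no such test.
- **That the safety tables would mislead in favor of allopurinol.** Clinic and 24-hour pressures are taken at Visits 2 to 5, and the change in 24-hour pressure is compared between phases, so falls are seen. The Table 7 summary is descriptive, and its description does not mention treatment.
- **That the asymmetry can be sized from the 3.7 mmHg difference and the SD of 8.5 mmHg in the sample-size section.** Those figures are a detectable difference and a spread for 24-hour means, not for single clinic readings. The documents give neither a clinic placebo mean nor a low cut-off that counts as harm. Nor is every systolic reading of 140 or more an adverse event: the grade adds that medical intervention is called for, the event must be new or worsened, and entry allows systolic values up to just under 160.

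**Conclusion.** The Nervous row in Table 8 is wrong as written: a mild symptomatic event has no valid grade. This rests on reading the parts of each cell together and on Table 8 being the rule that graders use. The defect covers one grade in one row, but it applies to every mild symptom reported under that row. How many there would be cannot be estimated from the documents. The rule is the same in both treatment phases, so the text alone shows blurred severity grading, not a bias toward either treatment. Severity is minor.

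The missing low-pressure row is real but secondary. Hypotension is not among the allopurinol risks listed under Risks and discomforts, so its relevance is inferred from the trial's own hypothesis and from the calcium channel blocker amendment. Adding a row is a reasonable improvement, not the correction of an error.

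**What to change.** **Needed.** In Table 8, replace the Nervous mild wording with that of the Other and Itch rows: "Asymptomatic or mild symptoms; clinical or diagnostic observations only; intervention not indicated". Check the option text behind the Nervous item on the REDCap form and make it match. If events have already been graded, review Nervous entries recorded as moderate or without a grade against the corrected wording, while still blinded. The cost is one phrase in the table, one check of the form and, where applicable, a short review of past entries.

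**Optional.** Add a decreased-blood-pressure row or a cardiovascular Other row to Table 8 and the form. The investigators should set any grades. Blood pressure is already measured at Visits 2 to 5, so nothing new is collected. The cost is one row and a few more mild adverse events recorded.
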